5.6 Study Enrollment Procedures

A copy of the institution's IRB-approved informed consent document and written justification for any changes made to the informed consent for this protocol must be on file at the before any participating institution may enter patients. Consent forms proposed for use at a participating institution must be reviewed and approved by the OHRS Regulatory Affairs Manager and all documents must be received (i.e., IRB approved documentation, IRB approved consent form, See Section 15.2 for a complete list of regulatory items).

Participating institutions will register patients through the OHRS Registration Desk

Patient demographic information, the signed and dated study-specific eligibility checklist and completed signature page of the consent form and additional source documents if requested by OHRS must be sent to the registration desk. Once the OHRS Registration Desk verifies eligibility, a unique patient study number will be issued. The patient will not be identified by name. This is the point that the patient is considered on study. Patients must not start protocol treatment prior to registration.

If a patient does not receive any protocol therapy, baseline data will be collected and submitted on the pre-study and follow-up electronic case report forms (eCRF). The reason for not starting protocol therapy will be documented in the "follow-up eCRF". Case report form completion instructions and training will be provided to each participating institution prior to study activation at the participating institution.

6. Study Parameters

The following tests and evaluations will be performed according to the schedule below. Baseline (i.e., pre-study) evaluations must be performed no longer than 4 weeks (+/- 3 days) prior to therapy, unless otherwise indicated in one of the footnotes below the table.

Evaluations	Pre- study	Every 4 weeks (prior to each cycle beyond cycle 1)	After the first 8 weeks (after first 2 cycles)	Every 12 Weeks	End of Treatment
Initial History and Physical	X ¹⁰				
Interim History and Physical ¹		X			X
Toxicity Assessment		X			X
ECOG Performance Status	X	X			X
Weight and Height ²	X	X			
CBC, differential, platelets	X^{10}	X ¹¹			X^{12}
Serum Chemistries ³	X^{10}	X ¹¹		***************************************	X^{12}
Liver Enzymes ⁴	X^{10}	X ¹²			X^{12}
EKG	X				
Radiographic Assessments ³	X			X	
Circulating Tumor Cells ⁶	X		X		
Correlative Blood Studies ⁶	X		X		
Archived Tumor Tissue ⁷	X				

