6.1 Efficacy Assessments

The primary efficacy endpoint is the clinical benefit rate of letrozole and sorafenib in this patient population. Clinical benefit rate ($CR + PR + SD \ge 6$ months) will be determined for each patient using definitions in RECIST to evaluate response.

will require copies of radiological scans performed during the study for all patients, and preferably on CD. A review of all radiological scans will be performed to verify or question the qualitative nature of the apparent response. For subjects with skin lesions, photographs should also be sent for review as well. Films and/or CDs should be mailed to:

7. Treatment Plan

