9.7 Confirmatory Measurement/Duration of Response

9.7.1 Confirmation

To be assigned a status of PR or CR, changes in tumor measurements must be confirmed by repeat assessments that will be performed no less than 4 weeks after the criteria for response are first met. In the case of SD, follow-up measurements must have met the SD criteria at least once after study entry at a minimum interval of not less than 8 weeks.

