16.2 Sample Size Justification

A historical study showed that single-agent letrozole in the first-line treatment of patients with hormone receptor-positive metastatic breast cancer had a clinical benefit rate of 50% compared to tamoxifen. The combination therapy of letrozole and sorafenib will not be considered of further interest if the true clinical benefit rate is less than or equal to 50%. We assume that this study will target a clinical benefit rate of 67% for identifying the combination therapy as active and worthy of further investigation. With these settings, the null hypothesis is that the clinical benefit rate of the combination therapy is less than or equal to 50%, and the alternative hypothesis is that the clinical benefit rate of 67% or more is of considerable interest. For the phase II part of the study, the sample size was calculated according to a single-stage design. The study will accrue a total of 58 patients, and the combination therapy will be accepted if there are at least 35 responders out of 58 patients. The design will have a 4.3% (< 5%) type-I error (false positive) rate and a power of 82.7% (> 80%) (i.e., 17.3% type-II error or false negative rate). The total number of evaluable patients to be accrued to this study is not expected to exceed 64 patients.

Phase I/II Trial of Letrozole (and Sorafenib as First-Line Therapy in Postmenopausal Women with Hormone Receptor-Positive Locally Advanced or Metastatic Breast Cancer PI:

The patients accrued in the Phase I dose escalation will be included in the Phase II portion if they receive the same dose. Evaluable patients for the phase I portion are defined as study-eligible patients who have received at least one cycle of treatment. Evaluable patients for the phase II portion are those who have received at least two cycles of treatment.

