16.3 Outcome Measures

Patients will be evaluated based on clinical benefit rate, as described in Sections 6 and Section 7. The rate of clinical benefit is defined as the proportion of patients who achieve a complete response, partial response, or stable disease ≥ 6 months. Time to progression will be calculated based on the time between the first day of treatment and the date of disease progression. Overall survival will be calculated based on the time between the first day of treatment and the date of death from any cause.

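### Section 16.2 defines a two-cycle evaluable set for phase II but does not say whether it is the denominator of the clinical benefit rate; if it is, the rate is expected to be biased upward

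*Combined protocol and SAP*

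**What the plan says.** Section 16.2 gives the accrual target, "The study will accrue a total of 58 patients", and the decision rule, "the combination therapy will be accepted if there are at least 35 responders out of 58 patients". It sets a ceiling for the whole study: "The total number of evaluable patients to be accrued to this study is not expected to exceed 64 patients". It then defines evaluability for phase II: "Evaluable patients for the phase II portion are those who have received at least two cycles of treatment". For phase I, evaluability needs eligibility and one cycle.

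Section 16.3 defines the endpoint without naming a set: "The rate of clinical benefit is defined as the proportion of patients who achieve a complete response", or the other qualifying outcomes. Section 16.4 describes time to progression, survival, serious adverse events and biomarkers, but gives no analysis or set for the clinical benefit rate. No section says how a patient with fewer than two cycles is counted, or whether she is replaced.

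Two other places bear on the denominator. Section 5.6 says of registration: "This is the point that the patient is considered on study". Section 6.1 says that clinical benefit "will be determined for each patient using definitions in RECIST to evaluate response". By contrast, Section 8 ties its one-dose set directly to the assessment of toxicity.

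**The concern.** The trial has one arm and compares one proportion with a fixed 50%. No control group would share the effect of a denominator choice, so that choice bears directly on the primary result. The plan leaves it open, and the only phase II set it defines is the more favourable of the two candidates.

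A set that requires two completed cycles selects on what happens after treatment starts. Those who fail earliest leave both numerator and denominator. The reported rate then describes patients who stayed on treatment for about two months, while the benchmark may describe everyone who started. With the set unnamed, the choice could also be made after the results are known.

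**Working it through.** **1. The plan's own figures.** Inputs from Section 16.2: n = 58, null rate 0.50, target rate 0.67, cut-off 35, stated type I error 4.3% and power 82.7%. With X ~ Bin(58, p):

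- P(X ≥ 35) = 7.40% at p = 0.50 and 88.7% at p = 0.67.
- P(X ≥ 36) = 4.35% at p = 0.50 and 82.65% at p = 0.67.

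The stated figures belong to a cut-off of 36. That mismatch is a separate point. Results below use 36, with 35 alongside where it helps.

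**2. Which set does the text mean?**

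- Towards all accrued patients: 58 is both the accrual target and the rule's denominator; a patient is on study from registration; benefit is determined for each patient.
- Towards the evaluable set: the two-cycle definition has no other stated use, and the ceiling of 64 is counted in evaluable patients. The ceiling is weak evidence, because it covers the whole study and phase I evaluability needs only one cycle.

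Neither reading is excluded.

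**3. Direction of the bias.** Two cycles are 2 × 28 = 56 days, longer with the delays allowed in Section 7.3. Section 9 schedules the first response assessment after cycle 3. For stable disease, Section 9.7.1 requires that "follow-up measurements must have met the SD criteria at least once after study entry at a minimum interval of not less than 8 weeks", and CR or PR must be confirmed at least 4 weeks after first being met. The Section 6 table schedules no scan at or after end of treatment. Footnote 9 asks for status every 3 months on the survival row and does not define status. A patient who leaves before two cycles could therefore rarely have documented benefit. Progression first seen at the week-12 scan stays in the denominator under either reading.

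**4. Effect on the estimate.** With x benefits among 58 treated and m early failures excluded, the reported rate is x/(58 − m).

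| Excluded m | x = 29 | x = 34 |
|---|---|---|
| 0 | 29/58 = 50.0% | 34/58 = 58.6% |
| 3 | 29/55 = 52.7% | 34/55 = 61.8% |
| 6 | 29/52 = 55.8% | 34/52 = 65.4% |

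**5. Effect on the decision.** Let d be the share excluded and b their benefit rate; both are assumed. If the 50% null is an all-treated rate, the rate among evaluable patients is p = (0.50 − d·b)/(1 − d). With b = 0, p = 51.0%, 52.6% or 55.6% at d = 2%, 5% or 10%.

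| How the rule is applied | d = 2% | d = 5% | d = 10% |
|---|---|---|---|
| 58 evaluable accrued, b = 0, cut-off 36 | 6.0% | 9.5% | 19.4% |
| Same, cut-off 35 | 9.8% | 14.8% | 27.5% |
| 58 evaluable accrued, b = 0.25, cut-off 36 | 5.1% | 6.5% | 9.9% |
| 58 treated, exact 5% test re-run on evaluable patients, b = 0 | 5.1% | 8.1% | 16.9% |
| 58 treated, fixed count, cut-off 36 | 4.35% | 4.35% | 4.35% |

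For the fourth row, the evaluable number is M ~ Bin(58, 1 − d), and the cut-off is the smallest count with an exact null tail of at most 5% given M. If b = 0.50, or if the 50% null was meant for evaluable patients, then p = 0.50 and nothing changes at any d.

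**6. Power if 67% was meant for evaluable patients.** With b = 0 the all-treated rate is 0.67(1 − d) = 65.7%, 63.7% or 60.3% at d = 2%, 5% or 10%. With 58 patients and cut-off 36, power is 76.5%, 65.4% or 44.8%.

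**The case against.** The strongest reply is that the rule already settles the matter. Section 16.2 uses 58 for both accrual and the denominator, so on its plain words all 58 count and the decision error is the same whatever share leaves early. This stands for the decision if the rule is applied that way. It does not settle the reported rate, and it leaves the two-cycle definition without a purpose.

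A second reply is that early exclusions may be few. Section 2.1.2.2 reports that 2% of letrozole patients stopped for adverse events over a whole trial, and Section 7.7 gives 3 and 1 of 451 sorafenib patients stopping for hand-foot reaction and hypertension. Against that, Section 2.1.3.2 gives a median treatment duration of 58 days for single-agent sorafenib in a previously treated population. None of these measures the share leaving this regimen before two cycles, so 2% to 10% is an illustration and not a bracket.

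A third reply is that the benchmark may itself be an evaluable-patient rate. Section 2.1.2.2 gives 50% for letrozole without a denominator, so this cannot be ruled out. If so, the type I error does not rise.

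A reader might go further and infer that the plan prescribes the two-cycle denominator, or that the false-positive rate is about 19%. The documents support neither: the set's use is not stated, and the 19.4% needs every condition in step 5 together with an assumed 10% share.

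**Conclusion.** The omission is certain: one phase II set is defined, its use is not stated, and no section names a set for the primary endpoint. If the two-cycle set is used, upward bias is expected because of the assessment schedule. This still rests on the assumption that excluded patients benefit less often than those kept, which is likely but not shown. The size is not known; in the examples, excluding three to six early failures adds 2.7 to 5.8 percentage points to a true 50%.

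The type I error rises only if three things hold together: 58 evaluable patients are accrued or the test is re-run on evaluable patients; the 50% null is an all-treated rate; and excluded patients benefit less than half the time. Otherwise only the estimate is affected. The point should be fixed before analysis. It does not show that the design fails.

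**What to change.** In Section 16.2:

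- Make the primary phase II set all eligible patients who start protocol therapy and count in phase II under the existing same-dose rule. State how Level 0 patients who escalate in cycle 2 (Section 7.4.1) are classed, since that rule does not say.
- Count anyone without documented CR, PR or SD of at least 6 months as having no clinical benefit, including those with no post-baseline disease assessment. Assessment should cover imaging, clinical measurement and photographs, because Sections 6.1 and 9.5.1 allow skin lesions to be followed without scans.
- Apply the 58-patient rule to that set, refer to it in 16.3 and 16.4, and keep the two-cycle set as a sensitivity analysis.
- State which population the 50% and 67% rates refer to. The documents do not settle this, so the team must. If 67% was meant for evaluable patients, restate the power for the all-treated set.

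The cost is wording in three sections and a somewhat lower reported rate. No extra patients are needed if 67% is an all-treated rate. If it is not, the power loss in step 6 applies. Restoring 80% power at an exact 5% level would take about 69, 91 or 156 patients at assumed shares of 2%, 5% or 10%. Those are the smallest sizes from which every larger size also meets both limits, a criterion that gives 58 when nobody is excluded.

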16.3 Outcome Measures

Patients will be evaluated based on clinical benefit rate, as described in Sections 6 and Section 7. The rate of clinical benefit is defined as the proportion of patients who achieve a complete response, partial response, or stable disease ≥ 6 months. Time to progression will be calculated based on the time between the first day of treatment and the date of disease progression. Overall survival will be calculated based on the time between the first day of treatment and the date of death from any cause.

16.4 Analysis

Time to progression and overall survival will be summarized using the standard Kaplan-Meier method. The frequency of serious adverse events as outlined in Section 8 will be described by summary statistics. Biological end points obtained from biopsy specimens are likely to be assessed semi-quantitatively, and compared using nonparametric methods to determine correlations with tumor response and disease progression.

17. Human Subjects

17.1 Subject Population

Postmenopausal women with previously untreated hormone receptor-positive locally advanced or metastatic breast cancer may participate in this trial if they meet the eligibility criteria. The inclusion and exclusion criteria detailed in this protocol are designed to exclude patients solely for medical reasons. Study participants will be patients who are receiving care for their disease at the affiliated medical oncology practices and community hospitals. The Principal Investigator and OHRS research personnel will closely monitor the status of the study (and individual patient data) at all centers. Males will not be eligible for this study. Breast cancer in men is rare and the efficacy of aromatase inhibitors in males is limited.

17.2 Potential Risks

All care will be taken to minimize side effects, but they can be unpredictable in nature and severity. Reported side effects of letrozole include headache, nausea, vomiting, peripheral edema, hot flashes, fatigue, hair thinning, bone pain, back pain, arthralgia, and dyspnea. Most of these side effects that were observed in patients who received letrozole in clinical studies were not considered serious and were generally mild to moderate. Reported side effects of sorafenib include hand-foot syndrome, diarrhea, fatigue, hypertension, pain and rash and were noted to be mainly mild to moderate. Grade 3 and 4 reactions were noted to be uncommon and seen as elevations in serum amylase and lipase levels (with corresponding symptoms of pancreatitis) and hand-foot syndrome.

Phase I/II Trial of Letrozole and Sorafenib as First-Line Therapy in Postmenopausal Women with Hormone Receptor-Positive Locally Advanced or Metastatic Breast Cancer

This study may involve risks to patients that are currently unforeseeable. Patients enrolled in this trial will receive their treatment in an outpatient setting. In addition, monthly blood work will be taken to monitor side effects. Evaluations at each cycle to monitor the treatment of patients will be performed and recorded in the patient chart. For patients at the or at the affiliated sites who do not customarily receive their care at the affiliated institution, a local oncologist should be identified to monitor for complications and to improve long term care. Although no compensation is available, any injury will be evaluated and treated in keeping with the benefits or care to which patients are entitled under applicable regulations.

17.3 Consent Procedures

Informed consent must be obtained prior to commencing any research procedures. The PI shall seek such consent only under such circumstances that provide the prospective patient opportunity to consider whether or not to participate and that minimizes the possibility of coercion or undue influence. The information given to the patient, or the representative, shall be in a language understandable to the patient or representative. The informed consent document may not include any exculpatory language through which the patient or representative is made to waive any of the patient's legal rights or releases, or appears to release the investigator, the sponsor or the institution from liability for negligence.

The investigational nature and objectives of this trial, the procedures and treatments involved and their attendant risks, discomforts, and potential benefits will be carefully explained to the patient. This process will include a general description of the disease process, as well as a description of the patient's expected clinical course. Alternative therapies will be fully described, and outlined in the consent document. The patient will be asked to read the consent at his/her convenience and will be encouraged to ask questions. Enrollment on this study will only occur if the patient meets all eligibility criteria, is judged by the Principal Investigator or participating investigator to potentially benefit from the therapy, is willing to provide consent, and has signed the consent document. Moreover, any experimental invasive procedure will require a separate consent form (standard procedure consent form).

17.4 Potential Benefits

It is likely that a significant proportion of patients who participate in this clinical trial will receive direct clinical benefit because they will be receiving a drug that is commonly used for their disease. This benefit may be reduction in the size of their tumor, stability in the size of their tumor, and/or improvement in symptoms related to their disease.

As a result of participating in this trial, patients will receive evaluation and treatment of their tumor at the or at the enrolling or at the enrolling affiliated institution. The study drugs, sorafenib and letrozole, will be provided at no charge to enrolled patients. However, additional medical services will be billed to the patients and/or their insurance carriers in the customary way. The cost of correlative pharmacodynamic studies will not be billed to the patient or insurer.

Phase I/II Trial of Letrozole	and Sorafenib (as First-Line Therapy in Postmenopausal
Women with Hormone Receptor-P	ositive Locally Advanced	or Metastatic Breast Cancer
PI:		

17.5 Risk-Benefit Ratio

The potential benefit that may result from this study balances the potential risks to the patients. A multicenter Phase III trial indicates that letrozole is superior in efficacy to tamoxifen in the first-line treatment of postmenopausal women with hormone receptor-positive metastatic breast cancer. However, it is not clear whether the combination of letrozole and sorafenib is superior to letrozole alone, but the theoretical approach of targeting two pathways of tumor progression simultaneously is encouraging. This protocol may or may not be helpful to a specific patient, but the results may help the investigators learn about the administration and effectiveness of letrozole and sorafenib in breast cancer and may aid in the treatment of other patients. This research treatment is not curative, but may offer temporary control of the disease. Benefit cannot be promised nor can the chance of benefit be accurately predicted.

17.6 Gender and Minorities

The National Institute of Health and NCI have stressed the importance of gender and minority inclusion in clinical services and research. African Americans make up 11%, Hispanics 6%, and Asians 5% of the patients, respectively. The percentage of minority patients enrolled onto clinical research trials were 12% African-American, 6% Hispanic, and 6% Asian, respectively.

No person shall on the grounds of race, color or national origin, be excluded from participation in, be denied the benefits of, enrollment in this study. There is a restriction regarding the sex of the patient. Minorities are prevalent in the

18. Economic/Financial Considerations

Patients and/or their insurance carriers will be expected to pay for costs related to monitoring and follow-up. Patients will be expected to pay for any costs not paid by their insurance carrier. The cost of correlative studies will not be billed to the patient or insurer. Patients will not be expected to pay for the cost of letrozole and sorafenib.

The policies and procedures of that the results of this trial will be submitted for publication in a timely manner following the conclusion.

PI, and all co-authors prior to submission or use, must review any abstract or manuscript.

Phase I/II Trial of Letrozole	and Sorafenib	as First-Line Therapy in Postmenopausal
Women with Hormone Receptor-Pos	sitive Locally Advance	ed or Metastatic Breast Cancer
PI:		

References

American Cancer Society: Cancer Statistics. http://www.cancer.org, 2007

Appendix A

Performance Status Criteria

ECOG Performance Status Scale		Karnofsky Performance Scale	
Grade	Descriptions	Percent	Description
0	Normal activity. Fully active, able to carry on all pre-disease performance without restriction.	100	Normal, no complaints, no evidence of disease.
		90	Able to carry on normal activity; minor signs or symptoms of disease.
1	Symptoms, but ambulatory. Restricted in physically strenuous activity, but ambulatory and able to carry out work of a light or sedentary nature (e.g., light housework, office work).	80	Normal activity with effort; some signs of symptoms of disease.
		70	Cares for self, unable to carry on normal activity or to do active work.
2	In bed <50% of the time. Ambulatory and capable of all self-care, but unable to carry out any work activities. Up and about more than 50% of waking hours.	60	Requires occasional assistance, but is abl to care for most of his/her needs.
	nous.	50	Requires considerable assistance and frequent medical care.
3	In bed >50% of the time. Capable of only limited self-care, confined to bed or chair more than 50% of waking hours.	40	Disabled, requires special care and assistance.
		30	Severely disabled, hospitalization indicated. Death not imminent.
4	100% bedridden. Completely disabled. Cannot carry on any self- care. Totally confined to bed or chair.	20	Very sick, hospitalization indicated. Death not imminent.
		10	Moribund, fatal processes progressing rapidly.
5	Dead.	0	Dead.

